18. DEVIATIONS FROM ANALYSIS AS DESCRIBED IN THE PROTOCOL

Study Day for Screening will run from Day -28 to Day -1, versus the Protocol SOA which says Screening will be from Day -28 to Day 0.

FCP [REDACTED] will be *separately* modelled using MMRM models due to major differences in analytical methods between these laboratories. See [Section 16.4](#).

19. PROGRAMMING SPECIFICATIONS

All outputs will be produced using SAS version 9.4 or a later version. Detailed programming specifications are provided in the Mock Tables, Listings and Figures (TFLs) file.

20. LIST OF TABLES, LISTINGS, AND FIGURES

See Mock TFLs file.

22. APPENDIX I. MAYO SCORING SYSTEM

The Mayo score ranges from 0 to 12, with higher scores indicating more severe disease.

Stool frequency subscore: Each participant serves as his or her own control to establish the degree of abnormality of the stool frequency.

0=Normal number of stools for this participant

1=1 to 2 stools more than normal

2=3 to 4 stools more than normal

3=5 or more stools more than normal

Subscore: 0 to 3

Rectal bleeding subscore: The daily bleeding score represents the most severe bleeding of the day.

0=No blood seen

1=Streaks of blood with stool less than half the time

2=Obvious blood with stool most of the time

3=Blood alone passes

Subscore: 0 to 3

Findings on endoscopy (endoscopy subscore): The endoscopy subscore will be determined by qualified personnel at a central laboratory.

0=Normal or inactive disease

1=Mild disease (erythema, decreased vascular pattern)

2=Moderate disease (marked erythema, lack of vascular pattern, friability, erosions)

3=Severe disease (spontaneous bleeding, ulceration)

Subscore: 0 to 3

Physician's Global Assessment: The Physician's Global Assessment acknowledges the 3 other criteria, the participant's daily recollection of abdominal discomfort and general sense of well-being, and other observations, such as physical findings and the participant's performance status.

0=Normal

1=Mild disease

2=Moderate disease

3=Severe disease

Subscore: 0 to 3.

The following combinations of subscores are used in efficacy endpoints definitions:

Modified Mayo score (MMS): Endoscopy subscore + Rectal bleeding subscore + Stool frequency subscore;

Mayo Clinic score (MCS): Endoscopy subscore + Rectal bleeding subscore + Stool frequency subscore + Physician's Global Assessment;

Partial Mayo Score (PMS): Rectal bleeding subscore + Stool frequency subscore + Physician's Global Assessment.

23. APPENDIX II. RELATIONSHIP OF MFAS TO ENDPOINTS

Table 9. Relationship of Primary Endpoint and Key Secondary Endpoints to Post-Baseline Assessments Occurring at the Same Visit

	Primary Endpoint	Key Secondary Endpoints			
Non-Missing Assessments at the Same Post-Baseline Visit	Clinical Remission	Endoscopic Improvement	Symptomatic Remission	Histologic Remission	Endoscopic improvement-histologic remission
ES		☑			
Geboes				☑	
ES, Geboes					☑
RB, SF			☑		
ES, RB, SF	☑				

For example, in order for a participant to contribute non-trivially to Symptomatic Remission at Induction Treatment Period Week 13 (Visit 7), their RB and SF scores must both be available at the Week 13 visit, according to the Visit Windows described in [Section 9.6](#). Because such a participant contributes *at least one* complete post-baseline Induction Treatment Period set of assessments for Symptomatic Remission, they are members of mFAS at *all* Induction Treatment Period post-baseline visits for Symptomatic Remission. This is true even if (say) Symptomatic Remission cannot be determined at Week 8 (Day 57) because SF is missing at Week 8.

24. APPENDIX III. VISIT LABEL MAPPING

EDC underwent significant changes between Protocol versions 1.0/2.0 and ≥ 3.0 , and especially for the OLE study period. The following visit mapping is intended to ensure that ADaM datasets utilize a consistent set of visit labeling conventions for tabulation, listing, and graphical purposes.

Table 10. Visit Label Mapping

Period	FolderName (Visit)		FolderName Mapped	PK Endpoints per Protocol	PK Sampling		
					Predose	2, 4, and 6 hours postdose (1, 2, 4 hrs postdose for V1)	24 hours postdose
Induction	Screening		Screening				
	Visit 2 Week 0		Visit 2 Week 0	Week 0	X	X	
	Visit 3 Week 1		Visit 3 Week 1	Week 1	X		
	Visit 4 Week 4		Visit 4 Week 4	Week 4	X		
	Visit 5 Week 8		Visit 5 Week 8	Week 8	X		
	Visit 6 Week 10		Visit 6 Week 10				
	Visit 7 Week 13		Visit 7 Week 13	Week 13	X - PV >2		
Long Term Extension (LTE)	LTE Visit 8 Week 13		LTE Visit 8 Week 13				
	LTE Visit 9 Week 18		LTE Visit 9 Week 18	Week 18	X		
	LTE Visit 10 Week 26		LTE Visit 10 Week 26	Week 26	X		
	LTE Visit 11 Week 36		LTE Visit 11 Week 36	Week 36	X		
	LTE Visit 12 Week 52		LTE Visit 12 Week 52	Week 52	X		
Open Label Extension (OLE)		OLE Week					
Protocol > V2	OLE Visit 1 Week 0	0	OLE Visit 1 Week 0		X	X	X
Protocol V1	Visit 8 Week 13	0	OLE Visit 1 Week 0		X		
	OLE Visit 2 Week 1	1	OLE Visit 2 Week 1		X	X	X
Protocol V1	Visit 9 Week 14	1	OLE Visit 2 Week 1				
	OLE Visit 3 Week 4	4	OLE Visit 3 Week 4		X	X	X
Protocol V1	Visit 10 Week 18	5	OLE Visit 3X Week 5				
	OLE Visit 4 Week 8	8	OLE Visit 4 Week 8		X		

Period	FolderName (Visit)		FolderName Mapped	PK Endpoints per Protocol	PK Sampling		
					Pre-dose	2, 4, and 6 hours postdose (1, 2, 4 hrs postdose for V1)	24 hours postdose
	OLE Visit 5 Week 13	13	OLE Visit 5 Week 13		X		
Protocol V1	Visit 11 Week 26	13	OLE Visit 5 Week 13				
	OLE Visit 6 Week 18	18	OLE Visit 6 Week 18		X		
Protocol V1	Visit 12 Week 36	23	OLE Visit 6X Week 23				
	OLE Visit 7 Week 26	26	OLE Visit 7 Week 26		X		
	OLE Visit 8 Week 36	36	OLE Visit 8 Week 36		X		
	OLE Visit 9 Week 39	39	OLE Visit 9 Week 39		X		
	Visit 13 Week 52 / End of Treatment	39	OLE Visit 9 Week 39				
	OLE Visit 10 Week 51	51	OLE Visit 10 Week 51				
	OLE Visit 11 Week 63	63	OLE Visit 11 Week 63				
	OLE Visit 12 Week 75	75	OLE Visit 12 Week 75				
	OLE Visit 13 Week 91	91	OLE Visit 13 Week 91		X		
	OLE Visit 14 Week 103	103	OLE Visit 14 Week 103				
	OLE Visit 15 Week 115	115	OLE Visit 15 Week 115				
	OLE Visit 16 Week 127	127	OLE Visit 16 Week 127				
	OLE Visit 17 Week 143	143	OLE Visit 17 Week 143		X		
Other							
	Unscheduled Visit		Unscheduled Visit				
	Early Termination Visit		Early Termination Visit		X		
	1-Week Follow-Up		1-Week Follow-Up		X		
	2-Week Follow-Up		2-Week Follow-Up		X		

25. APPENDIX IV. RESCUE THERAPY

Ventyx team members will classify therapies (medications and/or procedures) as ‘rescue’ for UC prior to interim database lock and in a blinded manner. Rescue therapy identification will occur prior to the Induction Period Analysis database lock and read-out. The method for Ventyx team members to use to perform this classification is described in this section. Rescue therapy identification will assist in establishing intercurrent events and Per Protocol analysis set membership.

Rescue therapies identified by Ventyx reviewers will be imported in statistical programming. Identified rescue therapies applicable to the Induction Period Analysis will be finalized before interim database lock and study unblinding. Only medications and medical procedures reported on the eCRFs will be assessed to determine whether they are rescue therapy for UC.

If rescue therapy exposure does not occur prior to efficacy assessment, then it is not considered a rescue therapy for the purposes of efficacy assessments occurring prior to rescue therapy exposure. The rules outlined below apply to both new use and increase in dose from Baseline.

Biologics with immunomodulatory properties

- Rule:
 - Any exposure after first dose of study treatment
- List of medications:
 - AntiTNF α antibodies:
 - ADALIMUMAB
 - CERTOLIZUMAB
 - CERTOLIZUMAB PEGOL
 - GOLIMUMAB
 - INFLIXIMAB
 - Other Biologics:
 - USTEKINUMAB
 - VEDOLIZUMAB

Non-biologics with immunomodulatory properties

- Immunosuppressants
 - Rules to consider for Visit 7 Week 13 efficacy endpoints
 - Must be discontinued > 2 weeks prior to Screening endoscopy

- Any treatment during the duration of the study
- List of medications:
 - MERCAPTOPYRINE
 - AZATHIOPRINE
 - TIOPURINE
 - METHOTREXATE
 - METHOTREXATE SODIUM
- 5-ASA Compounds
 - Rules to consider for Visit 7 Week 13 efficacy endpoints
 - After Screening and throughout time on study: any change from baseline
 - Discontinuation or reduction in dose allowed per Investigator judgement deems subject safety due to toxicity or medical necessity
 - Rectal route of administration must be discontinued prior to Screening
 - List of medications:
 - MESALAZINE
 - BALSALAZIDE
 - BALSALAZIDE DISODIUM DIHYDRATE
 - BALSALAZIDE SODIUM
 - OLSALAZINE SODIUM
 - SULFASALAZINE
 - BECLOMETASONE W/MESALAZINE
 - Routes:
 - ORAL
 - RECTAL
- Other small molecule immunomodulatory active agents
 - Rules to consider for Visit 7 Week 13 efficacy endpoints:
 - Must be discontinued ≤ 8 Weeks prior to Screening

- Any treatment during the duration of the study
- List of medications:
 - CICLOSPORIN
 - TACROLIMUS
 - TOFACITINIB
 - TOFACITINIB CITRATE
 - FILGOTINIB
 - UPADACITINIB
- Systemic glucocorticoids
 - Systemic glucocorticoids given via oral or rectal routes of administration
 - Rules to consider for Visit 7 Week 13 efficacy endpoints
 - After first dose of study treatment and up to and including Week 13: any increase from baseline (including new use) for more than 7 days
 - After Week 8: Any dose above baseline
 - After Week 13: dose may be tapered; however, if corticosteroid taper cannot be tolerated without recurrence of clinical symptoms of either UC or steroid withdrawal, corticosteroid dose may be increased (up to the dose at study entry if required), but tapering should be attempted again within 2 weeks
 - List of medications:
 - BETAMETHASONE
 - BETAMETHASONE DIPROPIONATE
 - BETAMETHASONE SODIUM PHOSPHATE
 - DEXAMETHASONE
 - DEXAMETHASONE SODIUM PHOSPHATE
 - DEXAMETHASONE VALERATE
 - METHYLPREDNISOLONE
 - METHYLPREDNISOLONE SODIUM SUCCINATE

- PREDNISOLONE
- PREDNISOLONE SODIUM PHOSPHATE
- PREDNISOLONE METASULFOBENZOATE SODIUM
- PREDNISONONE
- TRIAMCINOLONE
- HYDROCORTISONE
- HYDROCORTISONE ACETATE
- HYDROCORTISONE BUTYRATE
- HYDROCORTISONE SODIUM SUCCINATE
- Routes:
 - ORAL
 - RECTAL
- Systemic glucocorticoids given via parenteral routes of administration
 - Rule for Visit 7 Week 13 efficacy endpoints:
 - Any exposure after ≤ 2 weeks prior to Screening endoscopy
 - List of medications:
 - BETAMETHASONE
 - BETAMETHASONE DIPROPIONATE
 - BETAMETHASONE SODIUM PHOSPHATE
 - DEXAMETHASONE
 - DEXAMETHASONE SODIUM PHOSPHATE
 - DEXAMETHASONE VALERATE
 - METHYLPREDNISOLONE
 - METHYLPREDNISOLONE SODIUM SUCCINATE
 - PREDNISOLONE
 - PREDNISOLONE SODIUM PHOSPHATE
 - PREDNISOLONE METASULFOBENZOATE SODIUM
 - PREDNISONONE
 - TRIAMCINOLONE

- HYDROCORTISONE
 - HYDROCORTISONE ACETATE
 - HYDROCORTISONE BUTYRATE
 - HYDROCORTISONE SODIUM SUCCINATE
- Routes:
 - INTRAVENOUS
 - INTRAMUSCULAR
- Topical Glucocorticoids
 - Rules for Visit 7 Week 13 efficacy endpoints:
 - After first dose of study treatment and up to and including Week 8: any exposure above baseline (or new use) for more than 5 days
 - After Week 8: Any dose above baseline
 - List of medications:
 - BUDESONIDE (entocort, cortiment, uceris)
 - Routes:
 - ORAL
 - RECTAL
- Beclomethasone
 - Rules for Visit 7 Week 13 efficacy endpoints:
 - After first dose of study treatment and up to and including Week 8: Any increase above baseline for more than 5 days
 - After Week 8: Any dose above baseline
 - List of medications:
 - BECLOMETASONE
 - BECLOMETASONE DIPROPIONATE
 - BECLOMETASONE W/MESALAZINE
 - Routes:
 - ORAL
 - RECTAL

Medical procedures

- Leukocyte apheresis, other apheresis, and plasma exchange
 - Rule:
 - Any exposure after first dose of study treatment
 - List of medical procedures
 - APHERESIS
 - LEUKAPHERESIS
 - IMMUNOGLOBULIN THERAPY
 - IMMNOADSORPTION THERAPY
 - PLASMAPHERESIS
- Surgeries:
 - Rule:
 - Any exposure after first dose of study treatment
 - List of surgeries:
 - COLECTOMY (partial or total)
 - SIGMOIDECTOMY
 - COLOSTOMY
 - ILEOSTOMY

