3.5 Estimands

The primary and key secondary estimands are described in Table 1 below. The analyses will be performed on the Full Analysis Set (FAS) as defined in [Section 8](#). Other Secondary and Exploratory efficacy endpoints (specified in [Sections 16.3](#) and [16.4](#)) will generally be subject to the population, intercurrent event handling strategy, and population-level summary measures similar to the primary estimand. Supplementary analyses for the primary and key secondary

estimands will be performed using the FAS, Modified Full Analysis Set (mFAS), and Per Protocol (PP) populations.

Intercurrent events include exposure to rescue therapy for UC – see [Section 25](#), Appendix IV for the list of rescue therapies applying to this study. Additional intercurrent events include missed endoscopy at Visit 7 Week 13 for participants available to have a Visit 7 Week 13 endoscopy, and study discontinuation for either disease worsening or treatment-emergent adverse event with a preferred term indicating ulcerative colitis. See [Sections 16](#), [16.1.2](#), and [29](#) (Appendix VIII).

Participants will be evaluated for exposure to rescue therapy by Ventyx reviewers according to the guidelines presented in [Section 25](#), Appendix IV. Participants deemed to have received rescue therapy, and not experiencing other deviations preventing contribution to the primary and key secondary analyses of the primary and key secondary efficacy endpoints, will be treated as non-responders in those analyses; they will also be included in the Per Protocol analysis set. Use of concomitant medications and procedures that are not potentially effective for the treatment of UC will not be considered intercurrent events.

Table 1. List of Primary and Key Secondary Estimands

Estimand	Definition	Attributes			
		Population	Variable / Endpoint	Primary Intercurrent Event Handling Strategy	Population-Level Summary Measure
Primary Estimand	Efficacy of VTX002 on Clinical Remission (Modified Mayo Score) at Week 13	FAS	Proportion of participants with stool frequency (SF) subscore = 0 or 1, rectal bleeding (RB) subscore = 0, and endoscopic subscore (ES) \leq 1 (excluding friability)	Participants with any intercurrent events prior to Week 13 efficacy assessment will be treated as non-responders	Difference between VTX002 and Placebo with respect to population proportion of clinical remission at Week 13

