14.1 UC MEDICATIONS

Medications taken for UC will be considered prior UC medications if the start date of the medication is prior to the Informed Consent date. Otherwise, they are considered concomitant UC medications.

For the Induction Period Analysis, summaries of prior and concomitant UC medications will be separately presented by planned treatment group and overall for the Safety, FAS, mFAS, and PP sets. At study end, summaries will be presented by planned treatment group for FAS-ET population. Medications flagged as ‘rescue medications’ (see [Section 25](#), Appendix IV) will be considered concomitant UC medications and will be flagged in listings.

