16. EFFICACY

Controlled efficacy analyses are limited to the Induction Treatment Period. Efficacy endpoints may be computed for LTE and OLE study visits, but all hypothesis testing will be uncontrolled, resulting in nominal p-values and CIs only.

The study is designed to show superiority of VTX002 60 mg to placebo for the primary efficacy endpoint at Induction Week 13. Four key secondary endpoints are defined for this study and VTX002 30 mg is an important additional active drug dose of interest. Across the primary endpoint and key secondary endpoints, a total of ten (10) Induction Week 13 controlled hypothesis tests involving the two randomized VTX002 doses and placebo are planned. The family-wise error rate will be maintained at $\alpha = 0.05$ – see [Section 10.3](#) for details.

All controlled efficacy analyses (Week 13, Induction) will be primarily based on participant stratum at randomization (see [Section 10.2](#)) according to IWRS and for the FAS. Participants having MMS = 4 at baseline will be excluded from all efficacy analyses except the sensitivity analysis described in [Section 16.1.5](#). Additional sensitivity and/or supportive analyses will be performed as described elsewhere in this section. For composite scores such as MMS, if one or more components is missing from an analysis visit window the composite score is missing.

Blinded study team review will be used prior to Induction interim database lock and unblinding, to attribute a known Induction Week 13 non-response to participants having specific on-study experiences. Participants will be classified as non-responders in all responder-based efficacy analyses, including the primary endpoint, at all timepoints subsequent to the experience of the earliest of any of the following intercurrent events:

- Missed Visit 7 Week 13 endoscopy for participants eligible to have Visit 7 Week 13 endoscopy
- Discontinuation of the study during the Induction Treatment Period for either disease worsening or treatment-emergent adverse event having a preferred term indicating ulcerative colitis (UC)

- Exposure to rescue therapy for UC. See Appendix IV, [Section 25](#).

For a given participant, if efficacy outcomes (as opposed to components of outcomes) are available subsequent to an intercurrent event, they will be flagged as such. Participants may be included in the PP Set as long as other Per Protocol criteria are not violated.

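### SAP Appendix IV's 5-ASA trigger, read literally, scores a non-exempt 5-ASA reduction or stop as rescue, which does not fit the appendix's own scope

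*SAP*

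**What the plan says.** SAP Section 25 (Appendix IV) is the method that blinded sponsor reviewers use to decide what counts as rescue therapy. Its introduction sets the scope: "The rules outlined below apply to both new use and increase in dose from Baseline".

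Under 5-ASA compounds, among the rules for Week 13 endpoints, the trigger is "After Screening and throughout time on study: any change from baseline". The bullet below it reads: "Discontinuation or reduction in dose allowed per Investigator judgement deems subject safety due to toxicity or medical necessity".

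SAP Section 16 lists the intercurrent events, one of which is "Exposure to rescue therapy for UC. See Appendix IV". Its consequence is stated in the same section: "Participants will be classified as non-responders in all responder-based efficacy analyses, including the primary endpoint", at every timepoint after the event. Section 3.5 applies this to those the reviewers have classified: "Participants deemed to have received rescue therapy, and not experiencing other deviations preventing contribution" to the primary and key secondary analyses are treated as non-responders and stay in the Per Protocol set. Section 8 repeats the Per Protocol rule. Table 12 in Appendix VIII keeps non-responder scoring for intercurrent events under multiple imputation, copy reference and tipping point.

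Protocol Section 6.10.1 requires a stable 5-ASA dose and has the same exception for toxicity or medical necessity. It does not call a reduction rescue.

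**The concern.** A reduction or stop is a change from baseline, but it is neither new use nor a dose increase. The trigger and the scope sentence therefore give different answers for the same participant.

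Rescue is scored as non-response because a good outcome after added effective therapy cannot be credited to study drug. That reasoning does not extend to someone who takes less background 5-ASA and is still in remission at Week 13.

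At stake is the primary outcome of any such participant. A remission that was actually observed (rectal bleeding 0, stool frequency 0 or 1, endoscopy 0 or 1) would be overwritten. No planned sensitivity analysis relaxes the rescue rule, so none would restore it.

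**Working it through.** **Step 1. Compare the rules in Appendix IV.**

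- Scope sentence: new use and dose increase.
- Oral or rectal systemic steroids: increase from baseline, including new use, for more than 7 days; after Week 8, any dose above baseline.
- Budesonide: exposure above baseline, or new use, for more than 5 days up to Week 8; after that, any dose above baseline.
- Beclomethasone: increase above baseline for more than 5 days up to Week 8; after that, any dose above baseline.
- 5-ASA: any change from baseline, with no direction given.

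Among the rules that rest on a dose change, only the 5-ASA rule has no direction.

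**Step 2. Apply the text to cases.** Take a participant on stable oral mesalazine at baseline, with a change recorded on the eCRF at Week 4.

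| Change | Scope sentence | 5-ASA trigger with its exemption |
|---|---|---|
| Dose increased | Rescue | Rescue |
| Reduced for toxicity | Not rescue | Exempt |
| Stopped, no toxicity or medical need | Not rescue | Rescue |

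The readings differ only in the third row. If that participant has rectal bleeding 0, stool frequency 1 and endoscopy 1 at Week 13, the outcome is remission under one reading and non-response under the other.

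**Step 3. Check against the estimand.** Section 3.5 says that use of medications or procedures not potentially effective for UC is not an intercurrent event, and Section 16 speaks of exposure to rescue therapy. Both describe receiving treatment. Taking less of a background drug is not exposure to rescue.

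**Step 4. Reproduce the planning figure.** Inputs from SAP Section 6 and Appendix VII: 8% and 28%, two-sided alpha 0.05, power 0.80, normal approximation. The mean proportion is 0.18.

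n = [1.960 × √(2 × 0.18 × 0.82) + 0.842 × √(0.08 × 0.92 + 0.28 × 0.72)]² / 0.20² = (1.065 + 0.442)² / 0.04, which rounds up to 57 per arm. Power at 57 is 0.8019, against 0.802 stated. The proposed fix changes none of this.

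**Step 5. Size per case.** With 63 per arm, one recoded remitter moves that arm by 1/63 = 1.6 percentage points.

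**Step 6. Illustration only.** The documents give no rate of non-exempt 5-ASA reductions, so the number recoded is an assumption. Planning counts are 0.28 × 63 ≈ 18 and 0.08 × 63 ≈ 5. The test is an unstratified chi-square without continuity correction, not the planned stratified CMH test.

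| Recoded on 60 mg / placebo | Remitters | Difference (points) | p |
|---|---|---|---|
| 0 / 0 | 18 vs 5 | 13/63 = 20.6 | 0.003 |
| 1 / 0 | 17 vs 5 | 12/63 = 19.0 | 0.005 |
| 0 / 1 | 18 vs 4 | 14/63 = 22.2 | 0.001 |
| 1 / 1 | 17 vs 4 | 13/63 = 20.6 | 0.002 |
| 5 / 0 | 13 vs 5 | 8/63 = 12.7 | 0.042 |
| 6 / 0 | 12 vs 5 | 7/63 = 11.1 | 0.068 |

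The last two rows show only how extreme the assumption must be before the result at planning rates is lost. Nothing in the documents suggests such numbers.

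**The case against.** The strongest reply is that the lines can be reconciled. The scope sentence precedes every class rule and lists no exception. Read under it, the 5-ASA line would mean any new use or increase, with no minimum duration. The exemption bullet would then be a carry-over from Protocol 6.10.1. Appendix IV carries over other protocol conditions that cannot trigger rescue at Week 13, such as steroid tapering after Week 13. This reading is reasonable, and reviewers may well adopt it.

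It is not compelled. The scope sentence names new use and increase but does not say that nothing else counts. The exemption sits directly under the trigger, and as a rescue rule it has work to do only if other reductions and stops count. Two blinded reviewers could follow the same text and disagree.

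The objection on materiality largely stands. For an outcome to change, a reduction must be recorded on the eCRF, must breach Protocol 6.10.1, must fall outside a broad medical-necessity exception, must precede the Week 13 assessment, and must occur in an observed remitter. Such participants could also be found. Where outcomes "are available subsequent to an intercurrent event, they will be flagged as such", as Section 16 provides, the record is visible, and Section 14.1 says that rescue medications "will be considered concomitant UC medications and will be flagged in listings".

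A reader might infer that the plan treats every 5-ASA reduction as rescue. It does not, because reductions for toxicity or medical necessity are exempt and the scope sentence gives a basis for excluding the rest.

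**Conclusion.** The 5-ASA trigger is wrong as written, and the matter is minor. Taken literally, it can turn an observed remission into non-response in the primary and all other responder-based analyses, including Per Protocol and the three imputation analyses. That contradicts the appendix's scope, the exposure-based definition of the event, and the upward direction of the comparable steroid rules.

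The conclusion about wording rests on the text alone. The size rests on an unknown count, at 1.6 points per recoded remitter in an arm of 63. The count is likely small and may be zero.

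Two stronger inferences are not supported. One is that the rule biases the comparison between arms. Classification is blinded and finalised before the interim lock, and the documents do not show which arm would have more reductions, so no direction can be claimed. The other is that the primary result is at risk. The illustration needs six remitters recoded on 60 mg and none on placebo to pass 0.05, and the documents offer no support for that.

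**What to change.** Before the interim database lock, and while reviewers are still blinded:

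1. Reword the 5-ASA trigger to *any new use or dose increase from baseline*.
2. Send 5-ASA reductions or stops outside the Protocol 6.10.1 exception to the protocol-deviation review already planned in SAP Section 11.2, and keep the observed Week 13 outcome.

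If the sponsor does intend reductions to count as rescue, it should say so, give the reason, and correct the scope sentence to match.

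The cost is one line of SAP wording. No new data or analysis is needed, and the sample size and alpha are unchanged.

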27. Treatment with JAK inhibitors \leq 4 weeks prior to randomization
28. Use of IV corticosteroids and/or topical steroids \leq 2 weeks prior to Screening endoscopy. Alternative forms of steroids require consultation with the Medical Monitor.
29. Use of immunosuppressant drugs including thiopurines \leq 2 weeks prior to Screening endoscopy
30. Prior treatment failure with \geq 3 biologic agents with different mechanisms of action or \geq 2 biologics with different mechanisms of action plus a JAK inhibitor approved for the treatment of UC
31. Treatment with topical rectal 5-ASA or short-chain fatty acid enemas \leq 2 weeks prior to Screening endoscopy
32. Receipt of a live vaccine \leq 4 weeks prior to randomization and until 2 weeks post last dose. Approved nonlive vaccines, including severe acute respiratory syndrome coronavirus 2 (SARS-CoV-2), can be administered according to local vaccination standards.
33. Previous treatment with natalizumab
34. Previous treatment with lymphocyte-depleting therapies (eg, anti-CD4, cladribine, rituximab, ocrelizumab, cyclophosphamide, mitoxantrone, total body irradiation, bone marrow transplantation, alemtuzumab, daclizumab)
35. Previous treatment with D-penicillamine, thalidomide, dimethyl fumarate, or pyrimidine synthesis inhibitors
36. Treatment with IV immune globulin or plasmapheresis \leq 3 months prior to randomization

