8.3.1.2 Endoscopy

A flexible proctosigmoidoscopy or full colonoscopy, performed with a video endoscope following cleansing preparation (oral or rectal cathartic), will be performed as outlined in the SoA ([Section 1.2](#)).

Proctosigmoidoscopy/colonoscopy must be performed prior to randomization to treatment to allow central reader review (may take approximately 5 to 12 days) and confirmation of eligibility. Preferably, proctosigmoidoscopy/colonoscopy should be performed after other criteria for inclusion (eg, laboratory criteria) have been met.

To ensure quality data and standardization, the same endoscopist should be used throughout the study wherever possible. Endoscopy images/video will be obtained during each endoscopy and will be sent for central reading and determination of the Mayo ES. A detailed image review charter from the central reading laboratory will outline the endoscopic procedures, video recordings, and equipment.

For each participant, a video recording of the entire endoscopic procedure will be performed using an acceptable storage medium. Investigators are encouraged to send endoscopic recording by the following day after endoscopy. The endoscopic recordings will be read centrally in a blinded manner for mucosal lesions and endoscopic severity by a qualified gastroenterologist according to the image review charter. The ES will be evaluated by the Investigator and the central reader. The

central read will be used for determination of efficacy endpoints; however, treatment decisions will be made by the treating Investigator.

Repeat flexible proctosigmoidoscopy may be permitted by the Sponsor when the central reader indicates that the video endoscope data were acquired incorrectly or did not meet the minimal required quality standards.

The detailed instructions for endoscopy can be found in the Study Manual.

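### SAP Appendix IV mixes eligibility washouts into the rescue rules that code Week 13 non-response; the only parenteral-steroid rule opens before the first dose

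*SAP*

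**What the plan says.** SAP Section 25 tells sponsor reviewers how to classify therapies as rescue, blinded, before the interim lock. For glucocorticoids given by the intravenous or intramuscular route, the single rule for the Week 13 endpoints is "Any exposure after ≤ 2 weeks prior to Screening endoscopy". For biologics, and again for apheresis and surgery, the rule is "Any exposure after first dose of study treatment". The oral and rectal systemic steroid, budesonide and beclomethasone rules also begin after the first dose.

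Three other lines in the Appendix describe stopping a drug before treatment:
- Immunosuppressants, a list that includes methotrexate: stopped more than 2 weeks before the Screening endoscopy.
- Other small molecules (ciclosporin, tacrolimus and three JAK inhibitors): stopped at or under 8 weeks before Screening.
- Rectal 5-ASA: stopped before Screening.

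The consequence of a rescue flag is set elsewhere. SAP Table 1 (Section 3.5) says "Participants with any intercurrent events prior to Week 13 efficacy assessment will be treated as non-responders", with no start date. SAP Section 16 applies non-response "at all timepoints subsequent to the experience of the earliest of any of the following intercurrent events". Table 12 (Section 29) keeps that coding in the multiple imputation, copy reference and tipping point analyses, and Section 8 keeps it in the Per Protocol Set.

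On eligibility, Protocol Exclusion 28 bars "Use of IV corticosteroids and/or topical steroids" in the 2 weeks before the Screening endoscopy and adds "Alternative forms of steroids require consultation with the Medical Monitor".

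**The concern.** A composite strategy counts rescue as failure because needing rescue on treatment is itself a poor outcome. Exposure that ended before the first dose cannot be a consequence of study drug or a sign that it failed. The parenteral window follows the washout in Exclusion 28, which suggests that eligibility text was carried into a list of outcome rules.

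At stake is a correct and reproducible responder code for the primary and key secondary endpoints. Reviewers apply the Appendix by hand, and the Protocol (Section 6.10) collects medication history for at least 4 weeks before Screening, so pre-dose records will be in front of them. Two careful reviewers could code the same record differently. No planned imputation analysis would show the effect, because the rescue flag overrides the imputation in all of them.

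**Working it through.** **1. The plan's own figure.** Inputs from SAP Sections 6 and 28: 28% v 8%, two-sided 5%, normal approximation. Power = Φ{[d√n − 1.96√(2p̄(1−p̄))] / √(p₁(1−p₁) + p₂(1−p₂))}, with d = 0.20 and p̄ = 0.18. At n = 57: (1.510 − 1.065)/0.525 = 0.848, so power is 0.802, as the SAP states. At 63 analyzed per arm it is 84.0%.

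**2. Pre-dose part of the parenteral window.** Pre-dose days = 14 + days from Screening endoscopy to first dose. Days from first dose through Week 13 = 92.

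| Screening endoscopy | Basis | Pre-dose days | Share of window |
|---|---|---|---|
| Day -5 | shortest central read, Protocol 8.3.1.2 | 14 + 5 = 19 | 19/111 = 17% |
| Day -14 | ideal day, SAP Table 3 | 14 + 14 = 28 | 28/120 = 23% |
| Day -21 | 28-day Screening less 7 diary days, Protocol 8.3.1.3 | 14 + 21 = 35 | 35/127 = 28% |

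The first row uses the lower end of the read time that the protocol allows "to allow central reader review (may take approximately 5 to 12 days) and confirmation of eligibility". These are shares of calendar days, not of exposures.

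**3. Washout lines against the exclusions.**
- *Small molecules v Exclusion 24.* The protocol excludes treatment at or within 8 weeks before Screening. The SAP line, read literally, requires stopping within that period, so it faults those who stopped earlier. The direction is reversed.
- *Small molecules v Exclusion 27.* Suppose the line means an 8-week washout. With Screening starting between Day -1 and Day -28, the cut falls between Day -57 and Day -84. Exclusion 27 sets 4 weeks before randomization, about Day -28. The gap is 57 − 28 = 29 days to 84 − 28 = 56 days. Someone who stopped a JAK inhibitor in that band is eligible but breaches the SAP line. The 29-day end is a formal bound, since the diary and central-read requirements rule out a one-day Screening.
- *Methotrexate.* The SAP says 2 weeks before endoscopy; Exclusion 24 says 8 weeks before Screening. The SAP line is the looser one, so it faults no eligible participant; it is simply inconsistent.
- *Rectal 5-ASA.* The SAP anchors on Screening; Exclusion 31 anchors on 2 weeks before the endoscopy. Either can be met without the other, depending on the gap between Screening and endoscopy.

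**4. Scale.** The documents give no count of people with pre-dose parenteral exposure. Assume k of 63 per arm, k from 0 to 3, in equal proportion because exposure precedes randomization. Both rates shrink by (1 − k/63).

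| k | 60 mg v placebo | Difference (points) | Power, 63 per arm |
|---|---|---|---|
| 0 | 28.0% v 8.0% | 20.0 | 84.0% |
| 1 | 27.6% v 7.9% | 19.7 | 83.3% |
| 2 | 27.1% v 7.7% | 19.4 | 82.5% |
| 3 | 26.7% v 7.6% | 19.0 | 81.8% |

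At k = 3 the expected remitters miscoded are 3 × 0.28 = 0.84 on 60 mg and 3 × 0.08 = 0.24 on placebo. Losing one 60 mg remitter by chance moves 17 v 5 of 63 (p = 0.0049) to 16 v 5 (p = 0.0086; Pearson chi-square, uncorrected).

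**The case against.** The best defense is the SAP's own scope text. Section 25 says its rules concern new use and dose increases relative to Baseline, and Section 16 speaks of experiences on study. Under these, a finished pre-dose injection is not rescue. Section 14.1 can be read the same way: UC drugs begun before consent are prior medications, while rescue drugs "will be considered concomitant UC medications and will be flagged in listings". This shows the likely intent. It does not override a rule that states an explicit earlier opening, and Section 14.1 governs summaries and listings rather than responder coding. If the intent is post-dose, the rule contradicts it, and the wording still needs correcting.

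A reader might infer that an eligible participant given one intramuscular dose before the endoscopy would be enrolled as a fixed failure. The documents do not establish that. Consultation with the Medical Monitor is not permission. Inclusion 10 and Protocol Section 6.10.1 allow only oral corticosteroids, and Section 6.10.2 prohibits UC treatments outside the eligibility lists. A reader might also put the pre-dose window at up to 42 days by placing the endoscopy on Day -28. The 7 days of diary data needed before bowel preparation rule that out within a 28-day Screening.

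A fair objection to a bare first-dose start is that steroids given after the baseline endoscopy but before dosing can contribute to remission, and Exclusion 28 does not reach them. Coding those as failures is defensible. That stands, and the fix has to provide for it.

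For immunosuppressants and small molecules, a separate line already captures any use during the study, so the washout lines add little in practice.

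**Conclusion.** The wording defect is real; its consequence is small. The parenteral rule and the three washout lines put eligibility conditions among rules that determine the primary endpoint, and the 8-week line is both reversed and at odds with the JAK-inhibitor exclusion. Miscoding follows from the literal text but is not certain, since blinded reviewers may apply the scope sentence instead.

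The 0 to 3 per arm is an assumption, and the true number is probably at the low end. Even at 3, power stays above 80% under the planning rates. Because the exposure precedes randomization and the review is blinded, no systematic difference between arms is expected. A reader might infer bias toward or against VTX002, or a threat to significance; nothing in the documents supports either. Severity: minor.

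**What to change.** Before the blinded classification:

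1. Replace the parenteral rule with the one the Appendix already uses for biologics, "Any exposure after first dose of study treatment".
2. Delete the three pre-treatment stopping lines (immunosuppressants, other small molecules, rectal 5-ASA) from the rescue rules, and keep the existing on-study rules for each group.
3. Handle earlier use as eligibility deviations under Exclusions 24, 27, 28, 29 and 31. Record intravenous or intramuscular steroids given for UC between the Screening endoscopy and the first dose as a prohibited-medication deviation (Protocol 6.10.1 and 6.10.2), and run one sensitivity analysis coding those participants as non-responders.

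The cost is a few lines of Appendix wording, a little more deviation review and one extra analysis run. No new data are needed, and the test, the sample size and the composite strategy are unchanged.
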